#### CONFIDENTIAL AND PROPRIETARY

## Prospective multi-center study comparing REGENETEN in lieu of standard arthroscopic repair of high-grade (>50%) partial-thickness tears

 Number:

 REGEN.PUB.2018.09

 Version: 3.0, 10SEP2019

 Page: Page 40 of 105

smith&nephew

Item	Objective	Outcome Measure	Statistical Test	
	initial 3 months following index surgery.			
Secondary Objective #9	
 
undergo arthroscopic surgical treatment of high-grade (>50%) partial-thickness rotator cuff tears using REGENETEN use significantly less non-opioid prescription medication to treat the index shoulder compared to standard surgical repair over the initial 3 months following index surgery.
 
non-opioid prescription pain medication use from post-surgery to 3-months post- surgery. DDD will be used as the outcome measure.
 
		Generalized linear regression adjusting for baseline non- opioid prescription pain medication use and differences in baseline characteristics.	
Secondary Objective #10	To determine if participants who undergo arthroscopic surgical treatment of high-grade (>50%) partial-thickness rotator cuff tears using REGENETEN use significantly less opioids to treat the index shoulder compared to standard surgical repair over the 12 months from the index shoulder surgery.	Dose/duration of opioid use from post-surgery to 12- months post- surgery. DDD will be used as the outcome measure.	Generalized linear regression adjusting for baseline opioid use and differences in baseline characteristics.	
Secondary Objective #11	To determine if participants who undergo arthroscopic surgical treatment of high-grade (>50%) partial-thickness rotator cuff tears using REGENETEN use significantly less non-opioid prescription medication to treat the index shoulder compared to standard surgical repair over the 12 months from the index shoulder surgery.	Dose/duration of non-opioid prescription pain medication use from post-surgery to 12-months post- surgery. DDD will be used as the outcome measure.	Generalized linear regression adjusting for baseline non- opioid prescription pain medication use and differences in baseline characteristics.	
Secondary Objective #12	To determine if participants who undergo arthroscopic surgical treatment of high-grade (>50%) partial-thickness rotator cuff tears using REGENETEN have a shorter shoulder immobilization	Number of days in a sling	N/A	

#### CONFIDENTIAL AND PROPRIETARY

## Prospective multi-center study comparing REGENETEN in lieu of standard arthroscopic repair of high-grade (>50%) partial-thickness tears

 Number:

 REGEN.PUB.2018.09

 Version: 3.0, 10SEP2019

 Page: Page 41 of 105

smith&nephew

Item	Objective	Outcome Measure	Statistical Test	
	time compared to participants who had standard surgical repair.			
Secondary Objective #13	To determine if participants who undergo arthroscopic surgical treatment of high-grade (>50%) partial-thickness rotator cuff tears using REGENETEN return to work earlier than participants who had standard surgical repair.	Number of days to return to work estimated from date of surgery. Type of occupation is independent factor.	Generalized linear regression, adjusting for type of occupation and for differences in baseline characteristics.	
Secondary Objective #14	To determine if participants who undergo arthroscopic surgical treatment of high-grade (>50%) partial-thickness rotator cuff tears using REGENETEN return to driving earlier than participants who had standard surgical repair.	Number days to return to driving.	N/A	
Secondary Objective #15	To determine if participants who undergo arthroscopic surgical treatment of high-grade (>50%) partial-thickness rotator cuff tears using REGENETEN return to sports earlier than participants who had standard surgical repair.	Number days to return to sports.	Generalized linear regression, adjusting for baseline level of sporting activity and differences in baseline characteristics.	
Secondary Objective #16	To determine if participants who undergo arthroscopic surgical treatment of high-grade (>50%) partial-thickness rotator cuff tears using REGENETEN have a lower incidence of progression to full- thickness tears (diagnosed by MRI) compared to participants who had standard surgical repair at 12 months from the index shoulder surgery.	Incidence of full- thickness tears (diagnosed by MRI) within 12m from the index surgery.	N/A	
Secondary Objective #17	To determine if participants who undergo arthroscopic surgical treatment of high-grade (>50%) partial-thickness rotator cuff tears using REGENETEN have a lower incidence of progression of full-	Incidence of full- thickness tears (diagnosed by MRI) within 24m from the index surgery.	N/A	

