## 8.3.2 Secondary Endpoints

The secondary endpoints of this study include performance endpoints and economic endpoints. The performance endpoints are:

- 1. ASES score over initial 3 months following index surgery
- 2. Single Assessment Numeric Evaluation (SANE) score over initial 3 months following index surgery
- 3. ASES Visual Analog Scale (VAS) pain score over initial 3 months following index surgery
- 4. ASES score at 6, 12, 18 and 24 months following index surgery
- 5. SANE score at 6, 12, 18 and 24 months following index surgery
- 6. ASES VAS pain score at 6, 12, 18 and 24 months following index surgery
- 7. Constant-Murley score at 3, 6, 12 and 24 months following index surgery
- 8. Cumulative opioid use to treat the index shoulder over 3 months following index surgery
- 9. Cumulative non-opioid prescription medication use to treat the index shoulder over 3 months following index surgery
- 10. Cumulative opioid use to treat the index shoulder over 12 months following index surgery
- 11. Cumulative non-opioid prescription medication use to treat the index shoulder over 12 months following index surgery
- 12. Duration of shoulder immobilization following index surgery
- 13. Time to return to work by work type (sedentary; laborer)
- 14. Time to return to driving

This document contains information that is confidential and proprietary to Smith & Nephew PLC and Smith & Nephew, Inc. and is intended for use only by Smith & Nephew and its manufacturer. It shall not be reproduced or copied in whole or in part, nor shall the contents be disclosed by any means without prior written permission from Smith & Nephew, nor shall anyone make any use of it that is contrary to the expressed or implied wishes of Smith & Nephew.

Study Protocol—Device	Smith&nephew
	Number: REGEN.PUB.2018.09
lieu of standard arthroscopic repair of high-grade (>50%) partial-thickness tears	Version: 3.0, 10SEP2019
	Page: Page 26 of 105

- 15. Time to return to sports
- 16. Incidence of progression to full-thickness tear within 12 months following index surgery
- 17. Incidence of progression to full-thickness tear within 24 months following index surgery
- 18. MRI assessment of percent filling at 12 months following index surgery
- 19. MRI assessment of percent filling at 24 months following index surgery
- 20. Rotator cuff tendon thickness at 12 months following index surgery
- 21. Rotator cuff tendon thickness at 24 months following index surgery

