## Table 1: Study Procedures by Visit

*Pre-Op indicates pre-operative; Mo, month(s); SANE, Single Assessment Numeric Evaluation; ASES, American Shoulder and Elbow Surgeons Score including VAS Pain* 

†The ASES score and SANE will be completed every week (i.e., every 7±3 days) though 3 month follow-up. ‡Participant diaries will be used to document opioid and non-opioid prescription medication use, use of a sling, other related healthcare utilization (i.e. steroid injections, clinic visits, imaging, physiotherapy sessions, etc.) and return to work, driving, and sports. Participant diary will be updated weekly (7±3 days) through 3 month follow-up and monthly (30±7 days) thereafter until 12 months post-surgery.

\*The pre-op MRI is the participant's standard of care MRI and will not follow the study MRI Image Acquisition Protocol which is used for the 12 and 24 month MRIs. The pre-op MRI must occur within 6 months of enrollment into this study. All MRIs will be submitted to the imaging vendor per the Image Transfer Protocol.

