## 9.1.5 3 Month Visit (±30 days), 6 Month Visit (±30 days), 12 Month Visit (±30 days), 18 Month Visit (±60 days), and 24 Month Visit (±60 days)

- 1. Complete the ASES questionnaire (all visits), SANE questionnaire (all visits), and Constant-Murley assessment (3, 6, 12 and 24 month visits only).
- 2. Review diary entries for completeness with participant.
- 3. Document any health care utilization involving the index shoulder not recorded in the participant diary (3, 6, and 12 month visits).
- 4. Document any revision surgeries involving the index shoulder (all visits).
- If any adverse events, adverse device effects, or device deficiencies are observed or reported, they must be recorded as instructed in Section 12 – Adverse Events and Device Deficiencies (all visits).
- 6. MRI of index shoulder (12 month and 24 month visits).
- Instruct the participant on follow-up procedures, including returning for the next clinical follow-up (except for the 24 month exit visit).

This document contains information that is confidential and proprietary to Smith & Nephew PLC and Smith & Nephew, Inc. and is intended for use only by Smith & Nephew and its manufacturer. It shall not be reproduced or copied in whole or in part, nor shall the contents be disclosed by any means without prior written permission from Smith & Nephew, nor shall anyone make any use of it that is contrary to the expressed or implied wishes of Smith & Nephew.

Study Protocol—Device	Smith&nephew
lieu of standard arthroscopic repair of high-grade (>50%)	REGEN.PUB.2018.09
	Version: 3.0, 10SEP2019 Page: Page 30 of 105

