*Constant-Murley Score:* The Constant-Murley Score is a validated assessment of pain and shoulder functionality. The test is divided into four subscales: pain, activities of daily living, strength and range of motion (forward elevation, external rotation, abduction and internal rotation of the shoulder. At the end of the assessment, a score is obtained out of 100 points where higher scores indicate a higher quality of shoulder function. The score is obtained through a combination of participant-reported and objective (examiner-assessed) shoulder outcome measures.

*Duration of Shoulder Immobilization:* The duration of medically required shoulder immobilization following index surgery will be calculated based on the number of days in a sling, as reported in the participant diary.

*Cumulative opioid use:* Cumulative opioid use to treat the index shoulder from index surgery to 12 months will be calculated based on usage reported in the participant diary (name, dose, duration).

*Cumulative Non-opioid Prescription Medication Use:* Cumulative non-opioid prescription medication use to treat the index shoulder from index surgery to 12 months will be calculated based on usage reported in the participant diary (name, dose, duration).

*Time to Return to Work, Driving, and Sports:* Time from index surgery to return to ADLs will be calculated based on the date that participants report return to work (sedentary; laborer), return to driving, and return to sport as reported in the participant diary.

This document contains information that is confidential and proprietary to Smith & Nephew PLC and Smith & Nephew, Inc. and is intended for use only by Smith & Nephew and its manufacturer. It shall not be reproduced or copied in whole or in part, nor shall the contents be disclosed by any means without prior written permission from Smith & Nephew, nor shall anyone make any use of it that is contrary to the expressed or implied wishes of Smith & Nephew.

Study Protocol—Device	* smith&nephew
	Number:           REGEN.PUB.2018.09           Version: 3.0, 10SEP2019           Page: Page 33 of 105

*Incidence of Progression to Full Thickness Tear*. An independent reviewer will assess MRIs for evidence of progression to a full-thickness tear within 12 months and 24 months of the index surgery. All MRI assessments are detailed in the Image Review Charter.

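### Return to work (#13) and return to sports (#15) are time-to-return endpoints tested by regression on a day count, and the plan does not say how a participant without a return date enters the model

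*Combined protocol and SAP*

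**What the plan says.** Section 8.3.2 lists both endpoints as times, for example "Time to return to sports"; return to work is listed the same way, split by sedentary and laborer work. Section 9.2.1 says each time is "calculated based on the date that participants report return to work", or to driving or sport, as entered in the diary. The footnote to Table 1 limits that source: "Participant diary will be updated weekly (7±3 days) through 3 month follow-up and monthly (30±7 days) thereafter until 12 months post-surgery".

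Table 2 in section 10.4.2 then makes the outcome a number of days; for #13 it is "Number of days to return to work estimated from date of surgery". The test for #13 is "Generalized linear regression, adjusting for type of occupation and for differences in baseline characteristics". The test for #15 is "Generalized linear regression, adjusting for baseline level of sporting activity and differences in baseline characteristics". Return to driving (#14) has the same kind of day count but no test.

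Section 10.1 reports secondary outcomes descriptively unless otherwise stated, with selected ones tested as set out in section 10.4.2; #13 and #15 are among those tested. Section 10 describes itself as a brief account of a SAP still to be written. The supplied text does not mention censoring, a survival method, or a value for a participant with no return date.

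**The concern.** Two kinds of participant have no day count: those not back at the activity when the diary ends at 12 months, and those who leave before returning. The second group is to be expected. Section 7.7 bars further data collection once consent is withdrawn, section 7.7.1 does not replace participants who withdraw after surgery, and section 11 allows for 15% dropout.

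A regression with one day count per participant must omit these records or fill them in. Omitting them compares only those who returned, so selection is on the outcome itself. Filling in 12 months treats someone who left at month 2 as known not to have returned for ten more months.

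Faster return to activities of daily living is part of the study objective in section 4.1, and these are two of the secondary outcomes singled out for a test. A real difference could be missed, or one reported that is too large.

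**Working it through.** **Plan's own figure.** None exists for #13 or #15. The documents give no return rate, distribution or expected difference, so every input below except the 12-month diary limit is an assumption.

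**Inputs.** Follow-up 12 months (Table 1 footnote). Assumed: Weibull return times with shape k = 1 (exponential), 1.5 and 2; medians in ratio 1.5; complete follow-up at first; 30.44 days per month.

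**Formulas.** With median m:
- S(t) = exp(−(t/b)^k), where b = m / (ln 2)^(1/k).
- Restricted mean R = integral of S from 0 to 12 months. This counts everyone.
- Returners-only mean = (R − 12·S(12)) / (1 − S(12)). This is what remains if undated records are dropped.

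**One case in full.** k = 1, medians 3 v 4.5 months. Restricted means are 4.058 and 5.470; the difference is 1.412 months, or 43 days. Returners-only means are 3.528 and 4.249; the difference is 0.721 months, or 22 days. The share recovered is 0.721/1.412 = 51%.

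**Returners-only v restricted-mean difference in days (share recovered).**

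| Medians (months) | k = 1 | k = 1.5 | k = 2 |
|---|---|---|---|
| 2 v 3 | 25 v 37 (68%) | 34 v 35 (97%) | 32 v 32 (100%) |
| 3 v 4.5 | 22 v 43 (51%) | 39 v 49 (80%) | 47 v 48 (97%) |
| 4 v 6 | 18 v 44 (42%) | 35 v 56 (62%) | 50 v 61 (82%) |
| 6 v 9 | 13 v 41 (32%) | 23 v 55 (41.5%) | 34 v 67 (51%) |

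At 1 v 1.5 months the share is 95% to 100% for every shape. The loss follows the share not back at 12 months: for k = 1 that is 6.3% v 15.7% at 3 v 4.5 months and 25% v 39.7% at 6 v 9.

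**Cohorts differing only in who ever returns.** Suppose 95% v 85% ever return, with median 2 months among those who do. Returners-only gives 0 days. The restricted means are p·R + 12(1 − p). For k = 1, R = 2.840, so the difference is 0.10 × (12 − 2.840) = 0.916 months, or 28 days. For k = 2 it is 30 days.

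**Direction reversed.** k = 1.5, medians 2 v 3 months, but 85% of the faster cohort and 95% of the slower cohort ever return.
- Faster: 0.85 × 2.305 + 12 × 0.15 = 3.759 months.
- Slower: 0.95 × 3.452 + 12 × 0.05 = 3.879 months.
- Restricted-mean difference: 0.120 months, about 4 days.
- Returners-only difference: 3.419 − 2.305 = 1.114 months, or 34 days.

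With 90% v 95% ever returning, the figures are 34 v 18 days. Here dropping records overstates the benefit.

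**Assigning 12 months instead.** Assume a share q of each cohort leaves uniformly over the 12 months, unrelated to return, with k = 1 or 2. With q = 15% in both cohorts, the result is 96% to 107% of the true difference for medians from 2 v 3 to 6 v 9 months, and 106% to 111% at 1 v 1.5. With 10% leaving the faster cohort and 20% the slower, it is 104% to 124%, and 124% to 132% at 1 v 1.5. With equal return times (medians 2 to 6 months) and 10% v 20% leaving, it creates a false difference of 4 to 7 days.

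**The case against.** The strongest reply is that section 10 is expressly brief and rules for missing dates normally sit in the SAP. That stands as a limit: nothing here shows the final SAP will lack such a rule. It does not remove the point, because Table 2 already names the outcome and the model, and the SAP would have to change or add to them.

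Second, generalized linear regression is a family. Person-period binomial and piecewise-exponential Poisson models belong to it and handle censoring. A reader might infer that the planned method cannot use a participant without a return date; the documents do not support that. One day count per participant makes ordinary regression the likelier reading, but the gap is that the handling is unstated.

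Third, site staff are to "Review diary entries for completeness with participant" (section 9.1.5). This can recover an unrecorded date but cannot supply one for someone who has not returned.

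Fourth, size. The lowest shares come mainly from exponential times, which let return begin at full rate on the day of surgery, a weak model for work or sport. At shape 2 the share recovered is 82% to 100% until medians reach 6 v 9 months. That stands. Section 10.1 also treats secondary estimates as exploratory.

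**Conclusion.** The point holds as a gap in method that is cheap to close. Table 2 turns two time-to-return endpoints into day counts that do not exist for some participants, and the supplied text does not say what happens to them.

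If nearly everyone returns within a few months, the effect is negligible. If non-return by 12 months is common, half or more of the difference can be lost. These sizes rest entirely on assumed return times.

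A reader might infer that dropping non-returners always understates the difference. It does so when the slower cohort also has more non-returners, and overstates it when the faster cohort does. Treatment is chosen by the Investigator (section 8.2), so neither pattern can be assumed. Nor do the documents show that any result will in fact be biased.

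**What to change.** In Table 2 and the SAP, analyse #13 and #15 as time-to-event data: Kaplan-Meier curves with an adjusted Cox model or restricted mean time to 12 months. Keep the planned covariates, including occupation type for #13 and baseline sporting level for #15. Censor at the last diary entry or 12 months, whichever is first. Report per cohort the number and proportion without a return date, among participants doing that activity before surgery where this is recorded. Summarise #14 descriptively by Kaplan-Meier.

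The cost is wording plus a little more analysis; return dates and diary entries are already collected. Censoring at the last entry assumes that leaving early is unrelated to return. Restricting to those doing the activity before surgery may leave fewer than 59 per cohort, by an amount the documents do not give.

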#### CONFIDENTIAL AND PROPRIETARY

## Prospective multi-center study comparing REGENETEN in lieu of standard arthroscopic repair of high-grade (>50%) partial-thickness tears

Number: REGEN.PUB.2018.09 Version: 3.0, 10SEP2019 Page: Page 42 of 105

smith&nephew

ltem	Objective Outcome Statistical Measure		Statistical Test
	thickness tears (diagnosed by MRI) compared to participants who had standard surgical repair at 24 months from the index shoulder surgery.		
Secondary Objective #18	To determine if participants who undergo arthroscopic surgical treatment of high-grade (>50%) partial-thickness rotator cuff tears using REGENETEN have increased percent filling of the rotator cuff (based on MRI assessment) compared to participants who had standard surgical repair at 12 months from the index shoulder surgery.	Percent filling (based on MRI assessment) at 12-months post- surgery	N/A
Secondary Objective #19	To determine if participants who undergo arthroscopic surgical treatment of high-grade (>50%) partial-thickness rotator cuff tears using REGENETEN have increased percent filling of the rotator cuff (based on MRI assessment) compared to participants who had standard surgical repair at 24 months from the index shoulder surgery.	Percent filling (based on MRI assessment) at 24-months post- surgery.	N/A
Secondary Objective #20	To determine if participants who undergo arthroscopic surgical treatment of high-grade (>50%) partial-thickness rotator cuff tears using REGENETEN have improvements in rotator cuff tendon thickness (based on MRI assessment) compared to participants who had standard surgical repair at 12 months from the index shoulder surgery.	Rotator cuff tendon thickness (based on MRI assessment) at 12-months post- surgery.	Generalized linear regression adjusting for baseline tendon thickness and differences in baseline characteristics
Secondary Objective #21	To determine if participants who undergo arthroscopic surgical treatment of high-grade (>50%)	Rotator cuff tendon thickness (based on MRI	Generalized linear regression

#### CONFIDENTIAL AND PROPRIETARY

## Prospective multi-center study comparing REGENETEN in lieu of standard arthroscopic repair of high-grade (>50%) partial-thickness tears

Number: REGEN.PUB.2018.09 Version: 3.0, 10SEP2019 Page: Page 43 of 105

smith&nephew

Item	Objective	Outcome Measure	Statistical Test
	partial-thickness rotator cuff tears using REGENETEN have improvements in rotator cuff tendon thickness (based on MRI assessment) compared to participants who had standard surgical repair at 24 months from the index shoulder surgery.	assessment) at 24-months post- surgery.	adjusting for baseline tendon thickness and differences in baseline characteristics.
Secondary Objective #22	To determine if participants who undergo arthroscopic surgical treatment of high-grade (>50%) partial-thickness rotator cuff tears using REGENETEN have a statistically lower fatty infiltration of the rotator cuff (based on MRI assessment) compared to participants who had standard surgical repair at 12 months from the index surgery.	Goutallier classification of rotator cuff (based on MRI assessment) at 12-months post- surgery.	N/A
Secondary Objective #23	To determine if participants who undergo arthroscopic surgical treatment of high-grade (>50%) partial-thickness rotator cuff tears using REGENETEN have a statistically lower fatty infiltration of the rotator cuff (based on MRI assessment) compared to participants who had standard surgical repair at 24 months from the index surgery.	Goutallier classification of rotator cuff (based on MRI assessment) at 24-months post- surgery.	N/A
Secondary Objective #24	To determine if participants who undergo arthroscopic surgical treatment of high-grade (>50%) partial-thickness rotator cuff tears using REGENETEN have statistically improved rotator cuff integrity (based on MRI assessment) compared to participants who had standard surgical repair techniques at 12 months from the index surgery.	Sugaya score (based on MRI assessment) at 12-months post- surgery.	N/A

